11.1.	Investigator Authorisation Procedure.....	21
11.2.	Participant Protection	21
12.	SAFETY	21
12.1.	Adverse Event Reporting.....	21
12.2.	Serious Adverse Event Reporting	22
12.3.	Data Safety and Monitoring Committee (DSMC)	23
12.4.	Early Termination	23
13.	BLINDING AND UNBLINDING.....	23
14.	CONFIDENTIALITY AND STORAGE AND ARCHIVING OF STUDY	23
15.	TRIAL SPONSORSHIP AND FINANCING.....	23
16.	INDEMNITY	24
17.	KEY REFERENCES.....	24
18.	APPENDICES.....	24

Summary

Study title:

Novoglan-01 clinical trial to confirm the safety, efficacy and tolerability of the Novoglan product in treating adult phimosis

Protocol version: 2.1

Objectives

Primary objective: Confirm the efficacy of the Novoglan product as measured by the improvement in foreskin retraction against a standardised scale.

Secondary objectives: Confirm the safety and satisfaction with treatment as assessed by quality of life improvement and treatment tolerability.

Study design

Single arm, observational prospective trial

Planned sample size

Single cohort of 24 participants

Selection criteria

Participants 18 years or older consulting the Macquarie University Hospital and Princess Alexandra Hospital Urology Clinics with symptoms of adult phimosis, inability to fully retract the foreskin accompanied with pain or discomfort and including participants with prior frenuloplasty or Balanitis Xerotica Obliterans.

Study procedure

Enrolment Visit – Participant meets with physician who confirms eligibility criteria, measures the degree of phimosis and enrolls the participant into the study.

Study Visit 1 – Participant meets with clinical trial nurse for phimosis measurement, to complete the Quality of Life questionnaire and receive training and Novoglan materials and documentation.

Study Visit 2 and 3 – By phone between the clinical trial nurse and the participant at Week 1 and Week 4 post Study Visit 1 to review treatment progress.

Final Study Visit – At 6 to 8 weeks following Study Visit 2, participant meets with clinical trial nurse to measure foreskin retraction, complete the treatment tolerability questionnaire and the quality of life questionnaire – End of participant study

Statistical considerations Sample size calculation - As described in Section 8.
Analysis plan – As described in Section 8.

Duration of the Study

Completion by February 2022 from study start in September 2019

PREAMBLE – Clinical trial contributors and contact details

recommend the use of steroid creams or circumcision. The professional guidelines from the BAUS refer physicians to the guidelines published by the European Association of Urology (EAU) [EAU Guidelines, 2016] which address phimosis in the section dedicated to paediatric urology. The treatment recommendations include the use of steroid creams and if unsuccessful, the circumcision of the penis.

The main problem with using steroid creams to treat phimosis is the narrow range of stretching motion that will provide suitable stimulation for the foreskin to grow without exacerbating the inflammation or tearing of the foreskin. Recently, a new conservative treatment option, the Novoglan product, has shown promising results, with a very high success rate and satisfaction reported by users. The Novoglan product is designed to be used by participants 18 years and over. Its main component is a small balloon that can be inserted underneath the opening of the foreskin and progressively inflated while avoiding the complications frequently observed with the use of steroid creams. The Novoglan balloon is guided under the foreskin between the glans and the inner side of the foreskin (prepuce) using a purpose moulded rod. Once the balloon is in place the rod is removed and the stop cock and plunger is attached to the Novoglan device. The balloon is inflated by pressing the plunger. The procedure is painless and pressure is under the control of the user to ensure no discomfort. Foreskin cells are placed under tension and tight junctions are loosen under stretching leading to tissue adaptation and cell mitosis. This process increases the column of foreskin cells and increases the foreskin circumference. Treatment is continued for a period of 4 to 8 weeks until full normal retraction is achieved.

The Novoglan product is a medical device commercialised in Australia since 2006 and listed with the Australian Therapeutics Goods Administration (ARTG 168962). The Novoglan product has been used successfully in the Urology Clinic in the past year at Macquarie University Hospital but only with a few adult male participants. The observation of these few adult participant treatments indicated that the Novoglan product is simple and safe to use, effective at treating adult phimosis and comparatively inexpensive. It appears that the Novoglan product produces relief from the symptoms of phimosis in 3 to 4 weeks.

References, in order of citation, are as follows.

The prepuce.

1.2. Rationale for Performing the Study

The aim of the Novoglan-01 clinical trial is to conduct a scientific study in compliance with good clinical practice in order to confirm the safety, efficacy and tolerability of the Novoglan product as a conservative treatment for adult phimosis. This study is expected to provide evidence for the use of the Novoglan product as an alternative to steroid creams in the conservative treatment of adult phimosis and have the urological treatment guidelines for adult phimosis updated accordingly.

2. HYPOTHESIS

The hypothesis for the Novoglan-01 study is that the Novoglan product is an alternative conservative treatment for adult phimosis that is safe, efficacious and well tolerated by participants.

3. STUDY OBJECTIVES

3.1. Primary Objectives

The primary study objective is to measure the efficacy of the Novoglan treatment by measuring the degree of phimosis at the time of enrolment into the study and at the end of the participant study.

3.2. Secondary Objectives

The first of secondary objectives is to assess the safety of the Novoglan treatment by observing and reporting any treatment discomfort or adverse event mentioned by the participants during the treatment.

The second of secondary objectives is to confirm the participant satisfaction with the Novoglan treatment by assessing the improvement of quality of life reported by the participant and the treatment tolerability as reported by the participant at the end of the trial.

4. STUDY DESIGN

4.1. Design

The Novoglan-01 clinical trial is an investigator-initiated, single arm, non-randomised, observational, prospective study.

4.2. Expected Participant Numbers

The Novoglan-01 study is expected to enroll 24 participants.

4.3. Duration Of The Study

The Novoglan-01 study is expected to complete by February 2022 from a start in September 2019. The expected participant recruitment period would span the duration of the trial, starting with the trial start date and finishing 1 or 2 months before the expected end date.

4.4. Endpoints

Primary Endpoints

Primary endpoint – Efficacy of the device demonstrated by the improvement in foreskin retraction as measured using the Kikiros-inspired phimosis assessment scale.

Secondary Endpoints

First secondary endpoint – Safety of the device as evidenced by the reporting of any adverse effect or complication as observed and noted by the clinical trial team during the participant's treatment.

Second secondary endpoint – Participant satisfaction with the treatment as confirmed by treatment tolerability reported by the participant with a standardised treatment tolerability questionnaire and improvement in quality of life post-treatment as assessed by a standardised quality of life questionnaire before and after treatment.

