6.8. End of Study Treatment

At the end of a Novoglan-01 study and during the Final Study Visit, each participant will be:

- Measured for phimosis using the same measuring scale as used during Visit 1
- Surveyed for any adverse effect experienced during the study and not as yet reported
- Surveyed for quality of life using the same questionnaire as used during Visit 1
- Surveyed for tolerability of treatment using a purpose-designed questionnaire

Finally, at the end of each participant Final Study visit, all clinical trial documents related to the participant will be collected and stored in the ***Clinical Trial Master File*** for subsequent analysis and storage as per guidelines from the Australian Clinical Trial Handbook Version 2.0 dated March 2018.

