7. OUTCOMES

7.1. Definition of Outcomes

The expected outcomes from the Novoglan-01 study are as follows.

- Confirmation of the ability of the Novoglan product to effectively relieve phimosis as measured by foreskin retraction before and after treatment against the Phimosis Measurement Scale used at Study Visit 1 and Final Study Visit.
- Confirmation of the safety of the Novoglan treatment as evidenced by the lack of any severe adverse effect or any complication during treatment.
- Confirmation of the satisfaction of participants with the Novoglan treatment as measured by improved quality of life measured by questionnaire filled in by the participants before and after treatment.
- Confirmation of the tolerability of the Novoglan treatment as measured by the treatment tolerability questionnaire filled in by the participants during the Final Study Visit.
- Confirmation of the Novoglan treatment as a valid conservative first line treatment alternative to steroid creams in adult males presenting with phimosis.

Additionally, the publication of the Novoglan-01 study results at urology conferences and in a peer review journal is likely to encourage a review of clinical recommendations in the treatment of adult phimosis. Phimosis treatment guidelines published by the British Association of Urological Surgeons (BAUS) discourage the manual stretching of the foreskin and recommend the use of steroid creams or circumcision. The professional guidelines from the BAUS also refer physicians to the guidelines published by the European Association of Urology (EAU) which address phimosis in the section dedicated to paediatric urology.

Assuming a positive outcome from the Novoglan-01 study that demonstrates the safety, efficacy and tolerability of the Novoglan product in adult phimosis, the aim would be to:

- Convince the phimosis treatment guidelines published by the Urology Society of Australian and New Zealand (USANZ), EAU or BAUS to include a section dedicated to the treatment of adult phimosis.
- Convince the phimosis treatment guidelines published by the USANZ, EAU or BAUS to list the Novoglan product as a recommended conservative treatment for adult phimosis

Finally, the publication of the Novoglan-01 study results is likely to position MQ Health as the centre of reference for adult phimosis treatment in Australia. It is also likely to stimulate similar studies in Australia and overseas.

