8.2. Detailed Analysis Plan

The Novoglan-01 clinical trial involves the following measurement variables, which will be measured pre- and post-treatment:

Primary outcome variable (ordinal, scalar): Kikiros-inspired phimosis assessment scale (Kikiros, Beasley & Woodward 1993)

Secondary outcome variable (ordinal, scalar): A standardized treatment tolerability questionnaire

Secondary outcome variable (ordinal, scalar): A QoL scale questionnaire

The trial will also involve descriptive variables collected for each patient:

Physical parameters (e.g. age, weight, height – numerical variables)

Medical history (categorical, binary)

Record of Adverse Events (categorical, binary)

Evaluating Patient Descriptive Variables

The recommended analysis plan for the descriptive variables is to use a univariate analysis to contribute to the descriptive statistics of N. From there, tables showing frequency with medians, range, and standard deviations can be generated to describe the population.

Evaluating the Primary and Secondary Outcome Variables

An initial validation of each primary and secondary outcome variable will be applied using the Principal Component Analysis. If this analysis is successful, then each variable will be evaluated in an ordinal regression model (De Leeuw, Mair & Groenen 2017). If the outcome variables are to be evaluated at the same time, then a Multivariate Multinomial Logit Model will be applied (Bel & Paap 2014).

Further tests may be applied to evaluate any distributions and homogeneity within and between descriptive and outcome variables such as a Chi-Squared Test, Linear-by-linear Association Test, or Mann-Whitney U Test.

REFERENCES

- Bel, K. & Paap, R. 2014, A Multivariate Model for Multinomial Choices.
- R Development Core Team 2017, *R: A Language and Environment for Statistical Computing*, Vienna, Austria., R. Found. Stat. Comput., vol. 1.

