12. SAFETY

12.1. Adverse Event Reporting

The Novoglan product is a medical device, not a therapeutic product. As such, any adverse event encountered during the Novoglan-01 clinical trial should be recorded and processed as per the ***Therapeutics Goods Administration IRIS Reporting Scheme*** applicable to medical devices and which is detailed in the ***Novoglan-01 Safety Plan*** attached to this Study Protocol.

Devices Adverse Events - Definition

Any undesirable clinical occurrence in a participant whether it is considered to be device related or not, that includes a clinical sign, symptom or condition and/or an observation of an unintended technical performance or performance outcome of the device.¹

For devices is any adverse medical occurrence that:

- led to a death;
- led to a serious deterioration in health of a participant, including:
 - a life-threatening illness or injury;
 - a permanent impairment of body function or permanent damage to a body structure;
 - a condition requiring hospitalisation or increased length of existing hospitalisation;
 - a condition requiring unnecessary medical or surgical intervention; or
 - foetal distress, foetal death or a congenital abnormality/birth defect;
- might have led to death or a serious deterioration in health had suitable action or intervention not taken place. This includes:
 - a malfunction of a device such that it has to be modified or temporarily/permanently taken out of service; or
 - a factor deterioration in characteristics or performance) found on examination of the device.

An adverse event or serious adverse reaction can also be any event or experience which compromises the ethical acceptability of the protocol. This can be a non-medical event for clinical trials that are not medical or testing drugs or devices, such as those clinical trials conducted in different fields such as psychology.

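### Section 7.1 treats safety as confirmed if no severe effect or complication occurs, while sections 3.2 and 4.4 count any adverse effect, complication or discomfort, and section 8.2 does not list safety as an outcome

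*Protocol*

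**What the plan says.** The Protocol describes safety in several places.

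- **Section 4.4 (Endpoints), where safety ranks first among the secondary endpoints:** "Safety of the device as evidenced by the reporting of any adverse effect or complication as observed and noted by the clinical trial team". It sets no severity limit and no threshold.
- **Section 3.2 (Secondary Objectives):** safety is assessed by "observing and reporting any treatment discomfort or adverse event mentioned by the participants during the treatment". Again there is no severity limit, and discomfort is named.
- **Section 7.1 (Definition of Outcomes):** "Confirmation of the safety of the Novoglan treatment as evidenced by the lack of any severe adverse effect or any complication during treatment".
- **Section 8.2 (Detailed Analysis Plan):** the outcome variables are the phimosis scale (primary), and the tolerability and quality of life questionnaires (secondary). Adverse events appear only among the descriptive variables, as "Record of Adverse Events (categorical, binary").
- **Section 12.1 (Adverse Event Reporting):** the general definition for recording and reporting begins "Any undesirable clinical occurrence in a participant whether it is considered to be device related or not".
- **Summary, secondary objectives:** "Confirm the safety and satisfaction with treatment as assessed by quality of life improvement and treatment tolerability".

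The text shown defines neither *severe* nor *complication*. Section 12.1 lists outcomes of the seriousness type (death, serious deterioration and so on), but seriousness is not a severity grade.

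**The concern.** Sections 3.2 and 4.4 set out to describe everything untoward that happens to the men. Section 7.1 draws the conclusion, and it does so from part of that record: a non-severe effect that is not called a complication has no bearing on whether safety is confirmed. Section 8.2 does not close the gap, because it leaves the first secondary endpoint out of the outcomes to be evaluated.

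This matters because section 6.3 concedes that the product's safety has not yet been studied scientifically, and section 7.1 intends the results to persuade guideline bodies. A statement that safety was confirmed could accompany a substantial rate of adverse effects. It could also rest on a zero count that, with 24 men, is weak evidence.

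**Working it through.** **Inputs.** Participants: 24 (Summary, sections 4.2 and 4.5). Event rate, severity split and safety threshold: none given. The plan states no safety figure to reproduce, so the event counts below are assumptions, shown over a range.

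**Step 1: the same men under two sections.** Suppose x of 24 men have at least one mild effect, none severe and none classed as a complication. The section 4.4 rate is x/24. The exact (Clopper-Pearson) 95% limits are the 2.5% quantile of Beta(x, 24 − x + 1) and the 97.5% quantile of Beta(x + 1, 24 − x).

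| Men with a mild effect only (assumed) | Rate under 4.4 | Exact 95% CI | Events that count under 7.1 |
|---|---|---|---|
| 3 of 24 | 12.5% | 2.7% to 32.4% | 0 of 24 |
| 6 of 24 | 25.0% | 9.8% to 46.7% | 0 of 24 |
| 12 of 24 | 50.0% | 29.1% to 70.9% | 0 of 24 |

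In each row section 7.1, followed as written, confirms safety. The last column does not change as the rate rises from 12.5% to 50%.

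**Step 2: what 0 of 24 shows.** With zero events, the two-sided 95% upper limit is 1 − 0.025^(1/24) = 0.142, or 14.2%. So even a clean result on severe effects is compatible with a severe-effect risk of about one man in seven.

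**Step 3: how often the 7.1 criterion is met when the risk is real.** The chance of no event in 24 men at true risk p is (1 − p)^24, counting severe effects only and taking the men as independent:

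- p = 2%: 0.98^24 = 0.616, or 62%
- p = 5%: 0.95^24 = 0.292, or 29%
- p = 10%: 0.90^24 = 0.080, or 8%

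**Step 4: sensitivity to the number treated.** Section 8.1 speaks of recruiting 29 men to reach 24. If all 29 were supplied with the device, zero events would leave an upper limit of 1 − 0.025^(1/29) = 11.9%. The conclusion is the same.

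**The case against.** The best defence is that the endpoint is defined once, in section 4.4, and that the other passages do other jobs: section 3.2 states an objective, section 7.1 lists expected outcomes, and section 12.1 governs reporting. Section 4.4 sets no threshold and so gives no verdict. A report that 25% had a mild effect and none was severe would be an ordinary safety summary. Section 7.1 also fails on any complication, so mild irritation is not clearly excluded. Grading and summary measures may be in the Safety Plan, the case report forms or the Statistical Plan, which are attached to the Protocol but not shown here.

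Much of this stands, and it rules out several stronger readings that a reader might infer.

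- **Four or more incompatible definitions.** The documents do not support this. Section 12.1 is broader than section 4.4 but is not a rival endpoint. Sections 3.2 and 4.4 fit one data flow, since section 6.2 has the nurse phone the participant and record what he reports. In the Summary line, quality of life and tolerability can attach to satisfaction alone, as they do in sections 3.2 and 4.4.
- **Opposite verdicts in nearly every trial.** At least one mild event among 24 men is likely at moderate rates, but that is not two sections disagreeing, because section 4.4 gives no verdict.
- **A large gap between during treatment and during the study.** Section 6.8 asks at the Final Study Visit about effects "Surveyed for any adverse effect experienced during the study and not as yet reported", but sections 6.2 and 6.8 treat that visit as the end of treatment. A gap appears only if treatment means active device use, which section 4.4 does not say.
- **Section 7.1 cannot be scored.** A yes/no variable does not separate severe from mild, but the unseen Safety Plan and forms may record severity.

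The defence does not remove the mismatch. Grading in another document would make section 7.1 scorable, but would not make it agree with section 4.4 or add safety to the outcome variables in section 8.2.

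**Conclusion.** The point holds as an inconsistency within the Protocol. The endpoint and objective count any adverse effect, complication or discomfort. The confirmation in section 7.1 depends only on severe effects and complications, neither term being defined in the text shown. Section 8.2 treats adverse events as descriptive although section 4.4 ranks safety as the first secondary endpoint. The Summary line is loose wording rather than a separate contradiction.

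On size, with the assumed 6 of 24 men having mild effects only, the rate under section 4.4 is 25% (9.8% to 46.7%) while section 7.1 would confirm safety on 0 of 24. This requires that none of the six effects is classed as a complication. The limits of a zero count need no assumed event count: 24 men with no event leave an upper limit of 14.2%, and a true 5% risk yields that result in 29% of trials.

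**What to change.** Use one safety measure in sections 3.2, 4.4, 7.1 and 8.2: the number and percentage of men supplied with the device who have at least one adverse event as section 12.1 defines it, from supply at Visit 1 to the Final Study Visit, with an exact 95% confidence interval.

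- Show severe, serious and device-related events as subsets, and device malfunctions without clinical effect as a separate count.
- Define *severe* in the Protocol, or point to the definition if the Safety Plan has one.
- In section 7.1, replace the confirmation criterion with this rate and interval.
- In section 8.2, list the measure among the secondary outcome variables.
- Reword the Summary so that quality of life and tolerability attach to satisfaction only.

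The cost is wording in these sections and, if the case report forms lack them, fields for severity, seriousness and relation to the device. No visits or participants are added. The downside for the sponsor is a less favourable headline safety figure, because mild events count.

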4.5. Centres

The Novoglan-01 study will be running at two sites of the Macquarie University Hospital Urology clinic, New South Wales and at the Urology clinic of Princess Alexandra Hospital, Queensland, and a total of 24 participants are expected to be enrolled into the study.

5. STUDY PARTICIPANTS

5.1. Inclusion Criteria

The Novoglan-01 study inclusion criteria are as follows.

1. Male 18 or older referred to the urology clinic
2. Symptoms of adult phimosis with inability to fully retract the foreskin
3. Reporting of pain or discomfort

4. Potential participant may have Balanitis Xerotica Obliterans or undergone prior frenuloplasty
5. Willingness to provide informed consent and willingness to participate and comply with the study requirements.

